## DOCUMENT HISTORY

Document	Date of Issue	Summary of Change
Revised Protocol 06	14-Aug-2017	Incorporates Amendment 07
Amendment 07	14-Aug-2017	Clarify timing of collection of belatacept and comparator blood levels for clinically suspected AR, PML or PTLD. Update Procedural Outline Tables 5.1-2 and 5.1-3 to allow for collection of a blood sample for determination of the belatacept or comparator blood level at the time of any clinically suspected episode of acute rejection, PML or PTLD. Provide guidance regarding the evaluation and acceptable range for oral immunosuppressive treatment compliance. The type of T-cell responses to be tested for in cases of clinically suspected PTLD or PML was clarified as being “anti- viral ”, rather than specifically “anti- EBV ” in nature. Made modifications to secondary and exploratory endpoints to align the analyses of acute rejection with the statistical analysis plan, and corrected minor formatting and typographical errors throughout the protocol.
Revised Protocol 05	11-Nov-2016	Incorporates Amendment 06
Amendment 06	11-Nov-2016	Decrease number of sites and subjects. Statistical Sample Size Considerations updated. Clarification that all grades of acute rejection, will be included in analyses of the primary and relevant secondary endpoints.
Revised Protocol 04	19-Jan-2016	Incorporates Amendment 05
Amendment 05	19-Jan-2016	Clarification of antiviral prophylaxis requirement. Updates treatment and rescreening of living donor patients with a positive IGRA at screening. Revise protocol with recent administrative changes.
Revised Protocol 03	25-Aug-2015	Incorporates Amendment 04
Amendment 04	25-Aug-2015	Modification of the study design to remove an experimental treatment group: Thymoglobulin + belatacept + mycophenolate mofetil with rapid corticosteroid withdrawal, from the study design to eliminate a potentially higher risk of acute rejection. Updates to the randomization ratio, sample size per treatment group and sample size statistical determinations. Syntactical edits and clarifications to support the revised study design.
Revised Protocol 02	23-Dec-2014	Incorporates Amendment 03 and Administrative Letter 01
Amendment 03	23-Dec-2014	Modification of the study design, including the addition of an accepted standard of care active comparator treatment group and a change in the immunosuppressive medications paradigm. Updates to the research hypothesis and study objectives. Revisions to eligibility criteria. Addition of text for pregnancy precautions and U.S. reporting requirements from the CellCept Risk Evaluation and Mitigation Strategy. Clarification of the timing of randomization in relation to transplant surgery and initial dose of study drugs, and the temporal sequence of study drug dosing. Updates to the Time & Events Table including the addition of collection of safety and biomarker specimens; and clarifications to align the tables

Document	Date of Issue	Summary of Change
		with the protocol text and other studies within belatacept clinical study program. Update the requirements for evaluation of renal biopsy specimens to include assessments for acute antibody-mediated and as T-cell mediated rejection. Updates to the primary and secondary endpoints and statistical section to support the revised study design and to eliminate the allowance of crossover subjects. Minor edits and clarifications, including section numbering
Administrative Letter 01	12-Feb-2014	Clarify the everolimus trough sampling sequence during Year 1 of treatment.
Revised Protocol 01	21-Oct-2013	Incorporates Amendment 01
Amendment 01	21-Oct-2013	Modifications were made to the WOCBP definition, including FSH requirements and HRT washout period to align with BMS standards. Exclusion criteria were updated to remove annual mammogram, WOCBP criteria that do not apply. Updates to The Time & Events Table include removal of the Annual Mammogram to allow Investigators to use standard of care practices, the addition of a Neurological Exam and clarifications to align the table with the protocol text and with BMS belatacept program clinical studies. Protocol was updated with Neurological Exam requirements, modification of the clinical criteria and monitoring of PTLD. Modifications were made to the Events of Special Interest. Inclusion of Data Monitoring Committee. Minor edits and clarifications.
Original Protocol	28-Jun-2013	Not applicable

## SYNOPSIS

### Clinical Protocol IM103177

**Protocol Title:** Evaluation of Acute Rejection Rates in *de novo* Renal Transplant Recipients Following Thymoglobulin Induction, CNI-free, Nulojix® (belatacept) -based Immunosuppression

**Investigational Product(s) Dose and Mode of Administration, Duration of Treatment:**

**Belatacept** will be administered via intravenous (i.v.) infusion according to the following regimen:

Subjects randomized to the belatacept treatment group in the study will receive a belatacept regimen consisting of 10 mg/kg i.v. on Day 1 (started at least 12 but no more than 24 hours after completion of the initial induction dose of Thymoglobulin) and on Week 1 (Day 7), and then at weeks 2, 4, 8 and 12 post-transplant. After 3 months (Week 12), subjects will receive belatacept at the maintenance dose of 5 mg/kg i.v. every 4 weeks until completion of the trial.

**Thymoglobulin** will be administered via i.v. infusion according to the following regimen:

All subjects will receive Thymoglobulin in a dose of up to 1.5 mg/kg i.v. on Day 1 (Day of Transplant) and daily thereafter (or less frequently, as tolerated) to reach a total cumulative dose between 3.0 and 5.5 mg/kg. Premedication with i.v. methylprednisolone is required; as well as acetaminophen and/or antihistamine, per local practice, are recommended to reduce the risk of infusion reactions.

**Everolimus (EVL)** will be administered orally according to the following regimen:

Subjects randomized to receive EVL will receive an initial dose of 3.0 mg/day (1.5 mg bid) starting on Day 3. In subjects who experience delayed graft function (DGF), defined as the requirement for acute dialysis during the first post-transplant week, initiation of EVL may be delayed up to Day 7. In order to guide dose modifications, EVL pre dose trough levels should be obtained from the local laboratory per the protocol required schedule and 4 to 5 days after any change in dose. The dosing will be adjusted to keep pre-dose (C0) levels at 6 to 10 ng/mL for the initial 3 months post transplantation and at 4 to 8 ng/mL after 3 months and for the remainder of the study.

**Tacrolimus (TAC)** will be administered orally according to the following regimen:

Subjects randomized to the tacrolimus treatment group will receive the recommended total initial dose of TAC is 0.1 mg/kg/day orally in 2 divided doses and adjusted thereafter, on the basis of therapeutic drug monitoring, to target pre-dose (approximately 12-hour trough) blood concentrations of 4-11 ng/mL. Therapy with TAC may be initiated any time within the first 24 hours post-transplant, or delayed pending improvement in renal function, e.g., after the serum creatinine (SCr) concentration has decreased to  $\leq 4$  mg/dL (in the absence of dialysis). Initiation of dosing may be delayed up to Day 7, if, in the clinical judgment of the investigator, earlier initiation of TAC therapy is not in the best interest of the subject due to postoperative impairment of allograft function.

**Non-Investigational Product Dose and Mode of Administration, Duration of Treatment:**

**Mycophenolate Mofetil (MMF)** will be given orally according to the following regimen:

Subjects randomized to receive MMF will receive a daily dose of 0.5 to 2.0 g/day divided in 2 doses. The first dose of MMF should be administered preoperatively on the Day 1 (Day of Transplant). African Americans (Blacks) are eligible to be treated with higher doses, up to 3.0 g/day in divided doses. Doses can be given 4 times a day or can be reduced if intolerance occurs, per Investigator discretion. Subjects unable to tolerate the minimum allowable dose of 0.5 g/day may be converted to mycophenolate sodium, at doses equivalent to those for MMF, at the investigator's discretion.

**Corticosteroids:** will be administered throughout the study according to the following regimen:

This is a rapid corticosteroid withdrawal trial; corticosteroids are to be administered during the first week of study treatment only. All subjects will receive methylprednisolone (as the sodium succinate, as premedication prior to beginning each Thymoglobulin infusion to reduce the risk of infusion reactions), to be administered i.v. over approximately 30 minutes, as follows:

**1st Dose of Thymoglobulin:** 500 mg methylprednisolone i.v.

**2nd Dose of Thymoglobulin:** 250 mg methylprednisolone i.v.

**3rd Dose of Thymoglobulin:** 100 to 150 mg methylprednisolone i.v.

**Any additional doses of Thymoglobulin:**

**4th Dose of Thymoglobulin:** 60 mg methylprednisolone i.v.

**5th Dose and beyond of Thymoglobulin:** 30 mg methylprednisolone i.v. prior to each Thymoglobulin infusion

**Day 4 to Day 10:**

- **Subjects completing Thymoglobulin induction before Day 7** may receive prednisone, p.o. (or the equivalent) in lieu of the same dose of i.v. methylprednisolone:
  - **Day 4:** 60 mg prednisone p.o. (or equivalent)
  - **Days 5 through 7:** 30 mg prednisone p.o. daily (or the equivalent).
- **Subjects continuing to receive Thymoglobulin induction during Days 4-10** post-transplant should still be pre-treated with methylprednisolone i.v. as indicated above in lieu of p.o. prednisone.
- All corticosteroids are to be discontinued by Day 7, except for subjects still receiving thymoglobulin induction between Days 8 - 10; those subjects must discontinue corticosteroids after the final dose of thymoglobulin induction has been completed.

**Study Phase:** IIb

**Research Hypothesis:** A belatacept-based maintenance immunosuppressive regimen incorporating Thymoglobulin induction, EVL and rapid corticosteroid withdrawal will result in acceptable rates of AR and overall safety consistent with current standard of care in recipients of living and standard criteria deceased donor kidneys.

**Objectives:**

**Primary Objective(s)**

The primary objective is to assess the incidence of clinically-suspected and biopsy proven acute rejection (CSBPAR) at 6 months post-transplant in *de novo* renal allograft recipients treated with thymoglobulin induction, rapid corticosteroid withdrawal, and maintenance belatacept in combination with EVL, or maintenance TAC in combination with MMF.

**Secondary Objectives**

The effects of each immunosuppressant regimen on the rates of acute rejection, subject and allograft survival and allograft function will be evaluated as follows:

[figure not shown]
- The frequency and severity of acute rejection at 12 and 24 months post-transplant.
- Rates of subject and allograft survival at 6, 12 and 24 months post-transplant.
- Changes in renal function and severity of proteinuria at 3, 6, 12 and 24 months post-transplant.
- The frequency and type of donor-specific anti-HLA antibodies (DSA) detectable prior to, and at 12 and 24 months post-transplant.
- The safety and tolerability of each treatment regimen, as based upon the results of vital signs and safety laboratory assessments, and cumulative rates of adverse events reported at 3, 6, 12, and 24 months post-transplant.
- The frequency of cardiovascular and metabolic co-morbidities reported at 3, 6, 12, and 24 months post-transplant.

**Study Design:** This is a randomized, open-label, multicenter, parallel-group study to be conducted at approximately 20 sites in North and South America and the European Union. Approximately 70 subjects (n=35 per group) scheduled to receive a *de novo* kidney transplant will be randomized 1:1 ratio, to 1 of the following 2 treatment arms:

- 1) Thymoglobulin + Belatacept + Everolimus
- 2) Thymoglobulin + Tacrolimus + MMF

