### **3.6 Post Treatment Study Follow up**

Withdrawal of a subject from study medication does not imply that the subject is withdrawn from the study. Early Termination (ET) and Follow-Up Safety visit procedures must be completed per [Table 5.1-3](#) for all subjects who discontinue study drug. Information on subject and allograft survival will be collected for all subjects through 24 months post-transplant (at 6, 12 and 24 months).

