#### **8.4.2.2    *Subject and Graft Survival***

The endpoint of subject and graft survival at 6, 12 and 24 months post-transplant will be summarized within each treatment group using point estimates of the proportion of subjects surviving with a functioning graft, and the corresponding 95% CIs. The proportion of subjects who die, proportion of subjects who have a graft loss, and the proportion of subjects who experience the following outcomes will each be summarized using point estimates and 95% CI within each treatment group.

- Overall graft loss rates at 6, 12 and 24 months
- Rates of death with a functioning graft at 6, 12 and 24 months;
- Rates of pure (death-censored) graft loss at 6, 12 and 24 months.

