4.2 Secondary Endpoint

The two treatment groups will be compared for all secondary endpoints.

Acute Rejection

- Treatment differences in the incidence of CSBPAR at 6, 12 and 24 months post transplant, in the belatacept + EVL versus TAC + MMF treatment groups.
- Time to CSBPAR.
- Treatment differences in the severity grades and therapeutic modalities used to treat all episodes of CSBPAR at 6, 12, and 24 months post-transplant:
 - Severity: To be assessed by each local pathologist using the 2007 update to the Banff 97 classification of renal allograft pathology).

- Treatment regimen: Categorical analysis of CSBP/AR episodes by treatment received, including: a) corticosteroids; b) lymphocyte depleting therapy; c) renal replacement therapy; d) plasmapheresis; e) IVIg; f) rituximab.

Subject and Graft Survival

- Proportion of all subjects who survive with a functioning graft at 6, 12 and 24 months post-transplant.
- Proportion of all subjects who experience death by 6, 12 and 24 months post-transplant.
- Proportion of all subjects who experience graft loss by 6, 12 and 24 months post-transplant.
- Time to event analysis of death or graft loss.

Renal Function

- Absolute (mean and median) cGFR values at 3, 6, 12 and 24 months post-transplant, as determined from the 4-variable Modification of Diet in Renal Disease (MDRD) formula.
- The mean changes from Month 3 cGFR at 6, 12, and 24 months post-transplant.
- Slope of the change in cGFR from Month 3 to Months 6, 12 and 24 post-transplant.
- The mean urine protein to creatinine ratio ($U_{Pr/Cr}$) at 3, 6, 12 and 24 months post-transplant.

Donor Specific Anti-HLA Antibodies (DSA)

- The percentage of subjects with, and titers of pre-existing (pre-transplant) and *de novo* (post-transplant) anti-HLA DSA on Day 1 (pre-transplant, pre-dose), and at Months 12 and 24, respectively.
- Characterization of any *de novo* DSA detected by IgM and IgG classes, and by the presence or absence of complement fixing properties.

Safety and Tolerability of each Treatment Regimen

- Incidence of all AEs and SAEs at 6, 12, and 24 months post-transplantation.
- Incidence of ESI at 6 months, 12 months, and 24 months
- Description and incidence of clinically significant changes in vital signs.
- Description and incidence of laboratory test marked abnormalities.

Cardiovascular and Metabolic Co-Morbidities

- Incidence of New Onset Diabetes After Transplantation (NODAT) at 6, 12, and 24 months post-transplant.

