7 STATISTICAL ANALYSES

7.1 Modifications to the Analyses Specified in the Protocol

Due to the reduction in sample size resulting from premature termination of enrollment as of 31 December 2016, it has been deemed appropriate to revise selected statistical analyses specified in the study protocol [Section 8](#). The following modifications to and clarifications of the analyses have been made:

- 1) All analyses will be performed for the whole study treatment period (i.e. 24 months), including analyses at 6 or 12 months.

- 2) Treatment differences will be produced only for the endpoints specified in the sections of this SAP itemized below, instead for all study endpoints.
- 3) Analysis of acute rejections:
 - a) The treatment differences in the severity grades and therapeutic modalities will not be calculated.
 - b) The sensitivity analyses using the per-protocol population will be performed if there are at least 10% of subjects with a protocol deviation in either treatment groups.
 - c) The sensitivity analyses using the as-treated population will be performed if there are at least 10% of subjects in either treatment group for whom the as-randomized treatment group is different from the as-treated treatment group.
 - d) The sensitivity analysis using right censoring at the time of discontinuation from assigned therapy will not be produced. Acute rejections occurring more than 56 days after the last dose date will be flagged in the listing.
 - e) The descriptive summaries by treatment group for cGFR, graft and subject survival, donor specified antibodies, infection and malignancy at Month 12 for subjects with and without AR by Month 6, and at Month 24 in subjects with and without AR by Month 12, will not be produced. The information regarding these parameters will be included in listings that correspond to the specific analyses of these endpoints.
- 4) Analysis of subject and graft survival:
 - a) A listing including all subjects who died or lost their graft will be produced. Corresponding summaries, treatment differences and time to event analysis will be produced if there are at least 5 subjects across treatment groups who died or experienced graft loss during the 24 Month treatment period.
 - b) Any summaries mentioned above, if to be produced, will only be produced for the whole 24 Month treatment period. The corresponding analyses at 6 and 12 months will not be produced.

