 - c) Subject and allograft survival rates among those subjects who did and those who did not experience CSBPAR. This analysis will be produced only if there are at least 5 subjects across treatment groups who died or experienced graft loss during the 24 month-treatment period.
- 5) Analysis of the composite endpoints of CSBPAR, death, or graft loss will be produced only if there is at least one CSBPAR and at least one death or graft loss. These analyses will include the proportion of all subjects who experience CSBPAR, death, or graft loss at 12 and 24 months and a time to event analysis of the composite endpoint of CSBPAR, death, or graft loss.
- 6) All safety analyses will only be produced for the whole 24 Month treatment period. The corresponding safety analyses at 6 and 12 months will not be produced.
- 7) Analysis of immunogenicity: The protocol specifies summaries of titers of detectable anti-belatacept antibodies at Weeks 8, 12, and 24 post study termination (subjects who discontinue belatacept only). Instead of descriptive statistics, a listing will be provided for all positive subjects. Similarly, the analysis of descriptive statistics for titers of detectable anti-belatacept antibody will not be produced.

- 8) Analysis of any clinical consequences of CSBPAR (and associated changes in the expression of exploratory gene sets associated with acute rejection) at 6, 12 and 24 months post-transplant will be presented as follow:
 - a) The extent to which renal function recovered to the pre-rejection baseline will include the serum creatinine values related to CSBPAR in the corresponding listing.
 - b) The percentage of subjects who, post-CSBPAR, are reported to have developed infection or malignancy will not be summarized. Instead, a listing will be provided.
 - c) The percentage of subjects with, and titers of detectable, de novo (post-transplant) anti-belatacept antibodies will not be summarized. Instead, this information will be included in a listing of immunogenicity results with corresponding belatacept concentrations and selected laboratory parameters and events of special interest.
 - d) The subject and graft survival rates among those subjects who did, and those who did not experience CSBPAR will be provided only if there are at least 5 subjects across treatment groups who died or experienced graft loss during the 24 month-treatment period.

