8.3 Missing Data Handling

The following conventions will be followed while handling missing data. Only the relevant endpoints along with the specifics of the convention are included in this section.

Subject Survival and Graft Survival

Any subject (either randomized to belatacept or CNI) with unknown subject and graft survival status at Month 12 or Month 24, that is, whose last known follow-up date occurred prior to Day 334 or Day 698, respectively, will be considered as having experienced an event of graft loss or death, if at least one of the following criteria have been met during their documented period of follow-up post-randomization:

- Subject experienced at least one episode of BPAR at the time of, or prior to the last follow-up date.
- Subject was diagnosed as having PTLD at the time of, or prior to the last follow-up date.
- Subject's reason for discontinuation of study medication was lack of efficacy.
- A diagnosis of biopsy confirmed Polyomavirus associated nephropathy was reported as an adverse event before discontinuation.
- Subject's last calculated GFR (4-variable MDRD equation) was $< 15\text{mL}/\text{min}/1.73\text{m}^2$.

The remaining subjects with unknown patient and/or graft survival status at Months 12 or 24 (those who do not meet any of the above criteria) will be considered missing and not be included in the analyses or listing of the death and graft loss. For example, a patient with unknown status of the graft function and patient survival, and with no records of the above mentioned criteria, will not be considered in the numerator or denominator, while computing the percentage of death or graft loss.

Acute Rejection

Any acute rejection-free subject who is not followed-up through the entire event-counting period due to any reason will be considered as having no acute rejection during that period.

Renal Function

Missing cGFR values due to death or graft loss will be imputed with value of 0 and all other missing values will remain missing.

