8.4 Day Ranges for Analysis Time Points

Subjects do not always adhere strictly to the visit schedule timing in the protocol. Therefore the designation of the visits/months during the study will be based on the day of evaluation relative to day 1 of the trial (first dose date = study day 1) rather than the nominal visit/month recorded in the case report form (CRF).

The following rules apply to the derived visits depending on the specific endpoint. All endpoints analyzed over time will follow the analysis windowing specified in Table 8.4-1.

Table 8.4-1: Day Ranges for Analysis Time Points

At Month	Target Day	Day Range
1	28	1-56
3	84	57-112
6	168	141-196
9	252	225-280
12	364	337-392
15	448	421-476
18	532	505-560
21	616	589-644
24	728	701-756

Note: If a subject has more than one measurement recorded within the window for that time point, the measurement closest to the target day for that time point will be used. In any case in which both observations are equidistant from the target day, the later measurement will be used.

If data are collected at Month 2 (Week 8) then the day ranges are the following:

At Month	Target Day	Day Range
1	28	1-42
2	56	43-70
3	84	71-112

At Month	Target Day	Day Range
...		

In addition, the analyses for subject and graft survival, acute rejection related endpoints, NODAT and adverse events will follow the windowing below:

- Month 6: Defined as Day 1 to Day 168.
- Month 12: Defined as Day 1 to Day 364.
- Month 24: Defined as Day 1 to Day 728.

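### No survival or rejection/death/graft-loss proportion is planned at Month 6, where the primary endpoint counts early deaths and graft losses as rejection-free

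*Protocol*

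**What the plan says.** **Objective and endpoints.** The protocol synopsis and Section 1.3.2 set the objective "Rates of subject and allograft survival at 6, 12 and 24 months post-transplant". Protocol 8.4.2.2 plans the analysis with no event-count condition: "The endpoint of subject and graft survival at 6, 12 and 24 months post-transplant will be summarized within each treatment group using point estimates", with 95% CIs. SAP 3.2 repeats the objective, and SAP 4.2 still lists "Proportion of all subjects who survive with a functioning graft at 6, 12 and 24 months post-transplant".

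**Data.** Protocol 3.6 states that "Information on subject and allograft survival will be collected for all subjects through 24 months post-transplant (at 6, 12 and 24 months", including for subjects who have stopped study drug.

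**The change.** SAP 7.1 gives the reduced sample size as its reason. Item 4a makes survival summaries depend on at least 5 deaths or graft losses across both arms over 24 months. Item 4b limits any such summary to the full 24 months: "The corresponding analyses at 6 and 12 months will not be produced".

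**The composite.** SAP 7.1 item 5 and 7.6.2.2 make it conditional on a minimum of one rejection and one loss (of patient or graft). When that is met, the time points for the proportion are fixed as follows: "These analyses will include the proportion of all subjects who experience CSBPAR, death, or graft loss at 12 and 24 months". A time-to-event analysis is planned as well.

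**The primary endpoint.** SAP 8.3 says "Any acute rejection-free subject who is not followed-up through the entire event-counting period due to any reason will be considered as having no acute rejection" in that period. SAP 8.4 sets the period: "Month 6: Defined as Day 1 to Day 168".

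**The concern.** The primary measure is the proportion of each arm with CSBPAR by Day 168. A subject who dies or loses the graft before any rejection stays in the denominator as a non-event. An arm's primary rate is therefore no higher for having early losses of that kind. The usual safeguard is to print a loss proportion, or a composite that includes losses, next to the primary rate at the same time point. The protocol planned the first for Month 6 and the SAP withdraws it. The SAP's composite proportion starts at Month 12. Item 6 of SAP 7.1 also drops the 6- and 12-month safety analyses, so the safety summaries of death and graft loss do not supply the number. A named secondary objective is left without its planned proportion at two of its three times, and SAP 3.2 and 4.2 still promise it.

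**Working it through.** **1. Reproducing the plan's figures.** The plan states no loss rate or survival precision; its only figures here are the CSBPAR intervals in SAP 5. Clopper-Pearson limits are the 2.5% quantile of Beta(x, n-x+1) and the 97.5% quantile of Beta(x+1, n-x). With n = 35 and x = np:
- 3.8% (x = 1.33): 0.21% to 16.37%; stated 0.2% to 16.4%.
- 3% (x = 1.05): 0.09% to 15.14%; stated 0.1% to 15.1%.
- Difference, from Wilson score limits with 35 per arm: -13.17% to 11.32%; stated -13.2% to 11.3%.

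All reproduce. About one rejection per arm is expected, so one or two early losses per arm would be of the same order as the primary event count.

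**2. What is planned at each time.**

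| Quantity | Month 6 | Month 12 | Month 24 |
|---|---|---|---|
| CSBPAR proportion | yes | yes | yes |
| Survival with functioning graft, proportion | dropped | dropped | only if at least 5 losses |
| CSBPAR/death/graft loss, proportion | not planned | if at least 1 CSBPAR and 1 loss | same condition |

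**3. What a Month 6 composite would add.** Suppose one arm of 35 has 1 CSBPAR and k deaths or graft losses without prior rejection by Day 168. The primary rate is 1/35 = 2.9% (0.07-14.9%) for every k. The composite is (1+k)/35:
- k = 1: 2/35 = 5.7% (0.7-19.2%)
- k = 2: 3/35 = 8.6% (1.8-23.1%)
- k = 3: 4/35 = 11.4% (3.2-26.7%)
- k = 4: 5/35 = 14.3% (4.8-30.3%)

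These values of k are illustrations, not forecasts.

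**4. How often the survival analyses would run.** The Kaplan-Meier estimate of subject and graft survival needs at least 5 losses among 70. With an assumed 24-month loss rate q, P(X >= 5) = 1 - sum over x = 0 to 4 of C(70,x) q^x (1-q)^(70-x):

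| Assumed q | 2% | 3% | 5% | 7% | 10% |
|---|---|---|---|---|---|
| P(at least 5 losses) | 1% | 6% | 27% | 55% | 84% |

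**5. How often the composite would run.** It needs at least one CSBPAR and one loss. Taking the mean planning rate of 3.4% and independence, the chance is [1-(1-q)^70] x [1-(1-0.034)^70]. At q = 2% this is 0.757 x 0.911 = 69%; at 3% it is 80%, at 5% 89% and at 10% 91%. The chance of no CSBPAR at all among 70 is 0.962^35 x 0.970^35 = 9%. That uses 6-month planning rates. The SAP does not say over what period the condition is counted; over 24 months the chance of no rejection would be lower.

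**6. The corner case.** With no rejection in either arm, and four early losses in one arm and none elsewhere, the primary rate in that arm is 0/35 (0-10.0%, upper limit 1 - 0.025^(1/35)). The survival summaries are not produced (four losses, five needed), nor is the composite (no rejection). A Month 6 composite would read 4/35 = 11.4% (3.2-26.7%).

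**The case against.** Four arguments stand against a stronger reading.

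- **A reader might infer that no analysis covers Day 168.** That is not so. The composite has a time-to-event analysis, which spans Day 168 once there is one CSBPAR and one loss; the one-rejection, one-loss example meets that condition. The survival Kaplan-Meier also spans Day 168 when it runs. It shares its condition with the 24-month survival proportion, so whenever that figure appears, so does the timing of the losses.
- **A reader might infer that early losses would be hidden.** They would not. SAP 7.6.2.1 lists every death and graft loss unconditionally, and in arms of 35 a listing can be read case by case. Missing cGFR after a loss is set to 0 and enters the Month 6 renal summaries. SAP 7.7.1.3 tabulates serious adverse events by 6-month interval. None of these is a Month 6 loss proportion by arm.
- **A reader might take the SAP 8.3 and 8.4 conventions as proof that the SAP contradicts itself.** They are weak evidence. The Month 12 unknown-status rule can serve the Month 12 composite, and the Month 6 window is shared with CSBPAR and NODAT. The unreconciled text is in SAP 3.2 and 4.2, set against 7.1.
- **The change is disclosed and reasoned, in a descriptive study without tests.** This stands as to openness. As a justification it is incomplete: at the same sample size the SAP keeps CSBPAR proportions at all three times with 1.05 to 1.33 events expected per arm at Month 6, and keeps NODAT with CIs at 6, 12 and 24 months. SAP 7.2 already provides exact intervals for sparse counts.

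**Conclusion.** The point holds in limited form. No survival or composite proportion is planned at the 6-month primary time point, and the primary rate there counts a prior death or graft loss as rejection-free. Early losses reach the reader through a listing, through cGFR set to 0, and through time-to-event analyses that depend on event counts. The composite is suppressed when no rejection occurs, which is when the primary rate looks best.

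This rests on the text. The size does not: the documents give no loss rate, so the 2.9% against 5.7% contrast and the 2-10% range for q are assumptions, and the two example intervals overlap widely. Nothing here shows that the arms will differ in early losses or that the primary result will mislead. It is a cheap improvement to reporting that also answers a stated objective; it is not a flaw that invalidates the primary analysis.

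**What to change.** 1. Delete SAP 7.1 item 4b. That alone is not enough, because the five-loss condition in item 4a would often still suppress the estimates.
2. In SAP 7.6.2.1, report by arm the proportion surviving with a functioning graft by Day 168, Day 364 and Day 728 with exact CIs, and remove the five-loss condition for these proportions (here and in item 4a).
3. In SAP 7.1 item 5 and 7.6.2.2, give the composite proportion at 6, 12 and 24 months and drop the at-least-one-CSBPAR condition for the proportions. The remaining condition of at least one loss does no harm: with no losses the composite equals the CSBPAR proportion.
4. Extend the SAP 8.3 rule for unknown survival status to Month 6. The existing cut-offs fall 30 days before the window ends (364 - 334 = 30; 728 - 698 = 30), so the same offset would give Day 168 - 30 = Day 138.

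If the sponsor prefers to keep item 4b, SAP 3.2 and 4.2 should at least be reconciled with it.

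Cost: SAP wording and a few table rows with small counts and wide intervals. No new data are needed, since the protocol already collects survival status at these three times.
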